## **1. PROTOCOL SYNOPSIS SNDX-275-0601**

**Title:** A Phase 1b/2, Open-label, Dose Escalation Study of Entinostat in Combination with Pembrolizumab in Patients with Non-small Cell Lung Cancer, with Expansion Cohorts in Patients with Non-small Cell Lung Cancer, Melanoma, and Mismatch Repair-Proficient Colorectal Cancer

**Study Phase:** Phase 1b/2

**Indication:** Melanoma, Non-small Cell Lung Cancer (NSCLC), and Mismatch Repair-Proficient Colorectal Cancer”

**Primary Objective:**

**Phase 1b (Dose Escalation/Confirmation Cohorts):** To determine the dose-limiting toxicities (DLT) and maximum tolerated dose (MTD) or recommended Phase 2 dose (RP2D) of entinostat (SNDX-275) given in combination with pembrolizumab.

**Phase 2 (Expansion Cohorts):** To evaluate the preliminary efficacy of entinostat at the RP2D in combination with pembrolizumab in patients with melanoma, NSCLC, and mismatch repair-proficient colorectal cancer as determined by overall response rate (ORR), per the Immune-related Response Evaluation Criteria in Solid Tumors (irRECIST) in each cohort evaluated.

**Secondary Objectives:**

**Efficacy:** To evaluate the efficacy of entinostat in combination with pembrolizumab in patients with melanoma, NSCLC, and mismatch repair-proficient colorectal cancer as determined by secondary measures of efficacy per the Response Evaluation Criteria in Solid Tumors version 1.1 (RECIST 1.1) and irRECIST criterion, including:

- Clinical benefit rate (CBR) (i.e., complete response [CR]+partial response [PR]+stable disease [SD]) at 6 months
- Progression-free survival (PFS) status at 6 months
- PFS
- Overall survival (OS)

In patients who experience a response to treatment (i.e., CR or PR):

- Duration of response (DOR)
- Time to response (TTR)

**Safety:** To evaluate safety and the tolerability of entinostat in combination with pembrolizumab, as measured by clinical adverse events (AEs), laboratory parameters, and electrocardiograms (ECGs).

**Exploratory Objectives:**

**Hypothesis:**

Entinostat has been shown in preclinical models to reduce the number and inhibit the function of host immune suppressor cells in order to enhance the anti-tumor activity of immune checkpoint blockade. It is hypothesized that entinostat combined with pembrolizumab will result in an improved response rate for the combination compared to either agent alone. Preclinical study data suggest that entinostat specifically targets MDSCs and thus would improve the response to PD-1/PD-L1-blocking antibody (i.e., pembrolizumab) treatment. The Sponsor accordingly proposes to evaluate populations of MDSCs and other myeloid cells in peripheral blood and tumor tissues as well as basic T-cell function in patients, with the expectation that if the MDSC level is decreased, the response to antigens would be improved.

**Study Design:**

Study SNDX-275-0601 is an open-label, Phase 1b/2 study evaluating the combination of entinostat plus pembrolizumab in patients with advanced metastatic or recurrent NSCLC, melanoma or mismatch repair-proficient colorectal cancer. The study has 2 phases, a Dose Escalation/Confirmation Phase (Phase 1b) and an Expansion Phase (Phase 2), with the Expansion Phase utilizing a Simon 2-stage design (Simon 1989) for cohorts 1 and 4. For cohorts 2 and 3, the single proportion binomial test statistic is used to test for statistical significance. An additional cohort (Entinostat Monotherapy Immune Correlate [EMIC] Cohort) evaluating single agent entinostat followed by the combination will also be evaluated in patients with NSCLC in the Phase 2 expansion phase.

Regardless of phase, patients will be screened for study eligibility within 21 days before enrollment into the study. Patients who are determined to be eligible, based on screening assessments, will be enrolled into the study within 3 days of starting study treatment. With the exception of those in the EMIC cohort, patients will receive entinostat in combination with pembrolizumab on Cycle 1, Day 1 (C1D1), within 3 days from enrolling into the study.

A total of 15 patients will be enrolled in an EMIC Cohort. EMIC patients will be enrolled in the study within 3 days of starting study treatment on Day -14 (initiation of entinostat monotherapy) and will participate in a 2-week entinostat monotherapy period. The purpose of this 14-day lead-in phase is to obtain pre-and post-entinostat monotherapy correlative data in blood and tissue. After completion of the 2-week entinostat monotherapy period, patients in the EMIC Cohort will start entinostat in combination with pembrolizumab on C1D1. Patients in the EMIC Cohort will receive entinostat beginning at 5mg weekly for the monotherapy period, and then will receive entinostat in combination with pembrolizumab at the RP2D as identified in the Phase 1b Dose Escalation/Confirmation portion of the study.

A cycle is 21 days in length. During treatment, patients will attend study center visits and have study evaluations performed on C1D1, C1D8, and C1D15; D1 and D15 of C2; and on D1 of each cycle thereafter.

Fresh tumor tissue samples will be collected during the study as follows:

- During **screening** from **all** patients on a **mandatory** basis.
- On **C2D15 (+3 days)** on an **optional** basis from patients in the **Dose Escalation/Confirmation Phase**. All patients in the Dose Escalation/Confirmation Phase will be strongly encouraged to provide an optional biopsy in order to help understand dose-immune correlate effects.
  - On C2D15 (+3 days) on a **mandatory** basis from the **first 10 patients** (in total, across cohorts) in Stage 1 in the Expansion Phase, the first 10 patients in the EMIC Cohort, and the first 10 patients in the CRC Cohort. If, based on an interim review of tumor tissue data from the initial patients in

the Expansion Phase, such data are not considered informative, then tumor tissue samples will not be collected from subsequent patients on C2D15 (+3 days). Alternatively, if such data are considered informative, these tissue samples will be collected on C2D15 (+3 days) from subsequent study patients in the Expansion Phase.

Blood for immune correlates is to be collected from patients in the EMIC Cohort pre-dose on D-14, C1D1, C1D8, and C2D15. In all other cohorts, blood for immune correlates is to be collected pre-dose on C1D1, C2D1, and C2D15. Blood for protein lysine acetylation and for entinostat and pembrolizumab PK assessments will be collected according to the Schedule of Events.

Patients will have radiological disease assessments performed during screening and every 6 weeks (+/-3 days) (Week 6, Week 12, etc.). Disease will be assessed by computed tomography (CT), magnetic resonance imaging (MRI), and bone scans, as appropriate, and response will be assessed by the Investigator primarily using irRECIST.

Safety will be assessed during the study by documentation of AEs, clinical laboratory tests, physical examination, vital sign measurements, electrocardiograms (ECGs), and Eastern Cooperative Oncology Group (ECOG) performance status.

The maximum duration of treatment for this study is planned to be 2 years. If a patient permanently discontinues 1 of the 2 study drugs (either entinostat or pembrolizumab), the patient may continue to receive monotherapy for up to 2 years, unless alternate therapy is started or another discontinuation criterion is met ([Section 10](#)).

After discontinuation of both study drugs, patients will complete an End of Treatment (EOT) visit within 7 days after the last study drug dose and Safety Follow-up (F/U) visits 30 days and 90 days thereafter. After completion of the 30-day Safety F/U visit, patients who have not experienced progressive disease (PD) are to be followed every 2 months until PD and every 3 months thereafter until death or closure of the study by the Sponsor.

**Phase 1b (Dose Escalation/Confirmation):** The Dose Escalation/Confirmation Phase of the study, in which patients with NSCLC will be enrolled, employs a classical 3+3 design, with the determination of DLT and the MTD and/or RP2D based on entinostat in combination with pembrolizumab in C1.

Although decisions regarding dose escalation will be made primarily based on review of data from C1, safety data will also be collected from all patients continuing treatment and these data will be reviewed in an ongoing manner by the Sponsor Study Physician(s) including Medical Monitor, in consultation with the Investigators. Any detected cumulative toxicity may require later dose reductions and/or other changes to the dosing schedule, as appropriate, including further refinement of the RP2D.

**Dose Escalation:** The initial 3-6 patients will receive entinostat at a starting dose of 3mg on D1, D8, and D15 along with pembrolizumab 200 mg via intravenous (IV) infusion on D1 of a 21-day cycle. Assuming an acceptable safety profile, escalation to an entinostat dose of 5mg weekly is planned, keeping the pembrolizumab dose constant. However, based on evaluation of the safety and tolerability data of the previous dose level, it may also be decided that accrual will take place at an intermediate dose level or alternate dosing schedule. Toxicities will be assessed by the Investigator using the United States (US) National Cancer Institute (NCI) Common Terminology Criteria for Adverse Events (CTCAE), Version 4.03. The decision regarding whether to proceed to the next dose level will be made by the Sponsor Study Physician(s) in consultation with the Investigators after the majority of the safety assessments for each cohort are completed.

All patients within a cohort are to complete C1, have safety assessments performed through C2D1, and be assessed for DLT before enrollment of the next cohort may commence. If <33% patients within a cohort have a DLT (i.e., <2 of up to 6), then enrollment of the next cohort may commence with approval from the Sponsor Study Physician(s) in consultation with the Investigators. If  $\geq 33\%$  ( $\geq 2$  of up to 6) of patients within a cohort experience a DLT, then the DLT dose level will have been reached.

Patients who experience a DLT will be allowed to remain on study if they meet the following criteria: (1) the investigator believes it is appropriate for patients to remain on study; (2) the event has resolved and no longer meets the definition of DLT; and (3) the timeline for resolution falls within the protocol guidelines for dose delays.

Patients who complete C1 may continue on study as long as, in the Investigator's judgment, the patient is tolerating study treatment, is not at an increased safety risk, and continues to meet protocol eligibility criteria.

Six patients will need to be treated in a dose level for that dose to be considered for the Dose Confirmation stage. The recommended dose for Phase 2 investigation will be the higher of either 3 or 5mg weekly by mouth (PO) that results in less than a 33% incidence of DLT. The final determination of the optimal RP2D will consider both acute and cumulative toxicities; the incidence of required dose delays, reductions, and discontinuations; and the overall feasibility of administration in clinical practice.

**Dose Confirmation:** The prospective MTD/RP2D identified in the Dose Escalation Phase will be confirmed in 9 patients in the Dose Confirmation Cohort, to obtain additional AE, immune correlate, and anti-tumor activity data on entinostat in combination with pembrolizumab.

The decision regarding the RP2D will be made by the Sponsor Study Physician(s), based on a review of all data obtained from both the Dose Escalation and Confirmation Phases, with input from the Investigators.

After completion of the Dose Escalation/Confirmation Phase of the study, with identification of the MTD/RP2D, the Phase 2 portion of the study will commence.

**Phase 2 (Expansion):** In the Expansion Phase, entinostat in combination with pembrolizumab will be evaluated using the RP2D identified in the Dose Escalation/Confirmation Phase. Up to 4 Expansion Cohorts consisting of distinct subsets of patients with solid tumor cancers may be explored. Expansion cohorts 1 and 4 evaluated during the Expansion Phase will employ a Simon 2 stage design. Expansion cohorts 2 and 3 will employ single proportion binomial test (See **Sample Size Considerations**). The final decision about which Expansion Cohorts to study will be based on data from the Dose Escalation/Confirmation Phase, emerging clinical data from other studies, and/or nonclinical data. Expansion cohorts may include:

1. Cohort 1: NSCLC, with squamous cell or adenocarcinoma histology who have not been treated with a PD-1 or PD-L1 blocking antibody
2. Cohort 2: Patients with NSCLC (any histology) who have previously been treated with and unequivocally progressed on either a PD-1 or PD-L1-blocking antibody
3. Cohort 3: Patients with melanoma who have previously been treated with and unequivocally progressed on either a PD-1 or PD-L1-blocking antibody (i.e., pembrolizumab, nivolumab, MEDI4736, or GNE PDL1 [MPDL3280A])
4. Cohort 4: Patients with CRC (mismatch repair-proficient) who have not been previously treated with a PD-1 or PD-L1 blocking antibody

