#### **Sample Size Considerations:**

##### Dose Escalation/Confirmation Phase

Three to 6 patients will be enrolled in each dose cohort based on a standard Phase 1 dose escalation scheme. Each patient will participate in only 1 dose cohort. The total number of patients to be enrolled in the Dose Escalation/Confirmation Phase is dependent upon the observed safety profile, which will determine the number of patients per dose cohort, as well as the number of dose escalations required to achieve the MTD or RP2D.

A starting sample size of at least 3 patients per dose cohort - expanding to 6 patients in the event of a marginal DLT rate (33%) or to confirm a dose for the Confirmation Phase - is deemed to be a safe and conventional approach in the dose escalation of a novel oncologic agent. Assuming a true DLT rate of 5% or less, there would be a 3% chance that dose escalation would be halted in a given cohort (i.e., observing 2 or more patients with DLT). If a true DLT rate of 50% is assumed, then there would be an 83% chance that dose escalation would be halted in a given cohort.

As stated previously, a total of 9 additional patients will be enrolled at the potential RP2D in the Dose Confirmation Cohort to obtain additional AE, immune correlate, and anti-tumor activity data on entinostat at the MTD or other dose recommended for further investigation in Phase 2 (i.e., RP2D) in combination.

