Blood for immune correlates is to be collected from patients in the EMIC Cohort pre-dose on D-14, C1D1, C1D8, and C2D15. In all other cohorts, blood for immune correlates is to be collected pre-dose on C1D1, C2D1, and C2D15. Blood for protein lysine acetylation and for entinostat and pembrolizumab PK assessments will be collected according to the Schedule of Events. Blood for immune correlates and protein lysine acetylation is to be shipped on the same day of draw to the applicable laboratories with proper advanced notification according to the study laboratory manual.

Patients will have radiological disease assessments performed during screening and every 6 weeks (+/-3 days) (Week 6, Week 12, etc.) during treatment. Disease will be assessed by computed tomography (CT),

magnetic resonance imaging (MRI), and bone scans, as appropriate, and response will be assessed by the Investigator using irRECIST.

Safety will be assessed during the study by documentation of AEs, clinical laboratory tests, physical examination, vital sign measurements, ECGs, and Eastern Cooperative Oncology Group (ECOG) performance status.

The maximum duration of treatment for this study is planned to be 2 years. If a patient permanently discontinues 1 of the 2 study drugs (either entinostat or pembrolizumab), the patient may continue to receive monotherapy for up to 2 years, unless alternate therapy is started or another discontinuation criterion is met ([Section 10](#)).

After discontinuation of both study drugs, patients will complete an End of Treatment (EOT) visit within 7 days after the last study drug dose and Safety Follow-up visits 30 days and 90 days thereafter. After completion of the 30-day Safety Follow-up (F/U) visit, patients who have not experienced progressive disease (PD) are to be followed every 2 months until PD and every 3 months thereafter until death or closure of the study by the Sponsor.

**Phase 1b (Dose Escalation/Confirmation):** The Dose Escalation/Confirmation Phase of the study, in which patients with NSCLC will be enrolled, employs a classical 3+3 design, with the determination of DLT and the MTD and/or RP2D based on entinostat in combination with pembrolizumab in C1.

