## 5.3 Number of Patients

In the dose-escalation phase, 3 to 6 patients will be enrolled in each dose cohort based on a standard “3+3” Phase 1 dose escalation scheme. Each patient will participate in only 1 dose cohort. A total of 9 additional patients will be enrolled in the Dose Confirmation Cohort to obtain additional AE, immune correlate, and anti-tumor activity data on entinostat at the MTD or other dose recommended for further investigation in Phase 2 (i.e., RP2D) in combination.

Thus, the total number of patients to be enrolled in the Dose Escalation/Confirmation Phase is dependent upon the observed safety profile, which will determine the number of patients per dose cohort, as well as the number of dose escalations required to achieve the MTD.

In the Expansion Phase, up to 252 patients are planned to be enrolled among the 4 Expansion Cohorts (Section 5.1).

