### 8.2.1.1 Dose Escalation /Confirmation Procedure

#### Dose Escalation

Toxicities will be assessed by the Investigator using the NCI CTCAE, Version 4.03. The decision regarding whether to proceed to the next dose level will be made by the Sponsor Study Physician(s) in consultation with the Investigators, after the safety assessments for each cohort are completed.

All patients within a cohort are to complete C1, have safety assessments performed through C2D1, and be assessed for DLT before enrollment of the next cohort may commence. If  $<33\%$  patients within a cohort have a DLT (i.e.,  $<2$  of up to 6), then enrollment of the next cohort may commence with approval from the Sponsor Study Physician(s) in consultation with the Investigators. If  $\geq33\%$  ( $\geq2$  of up to 6) of patients within a cohort experience a DLT, then the DLT dose level will have been reached and the previous lower dose level will be considered the MTD. Patients who experience a DLT will be allowed to remain on study if they meet the following criteria: (1) the investigator believes it is appropriate for patients to remain on study; (2) the event has resolved and no longer meets the definition of DLT; and (3) the timeline for resolution falls within the protocol guidelines for dose delays.

If a DLT necessitates enrollment of additional patients into a cohort, the Sponsor Study Physician(s) in consultation with the Investigators, will review all safety data for that cohort after all patients have completed C1.

Although decisions regarding dose escalation will be made primarily based on review of data from C1, safety data will also be collected from all patients continuing treatment and these data will be reviewed periodically by the Sponsor Study Physician(s) in consultation with the Investigators. Any detected cumulative toxicity may require later dose reductions and/or other changes to the dosing schedule, as appropriate, including further refinement of the RP2D.

Patients who discontinue from the study for reasons other than study drug-related toxicity before completing C1 may be replaced.

Patients who complete C1 may continue on study as long as, in the investigator's judgment, the patient is tolerating the study treatment, is not at an increased safety risk, and continues to meet protocol eligibility criteria.

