## 12. STATISTICAL CONSIDERATIONS

### 12.1 Sample Size Estimation

#### 12.1.1 Escalation Phase

Three to 6 patients will be enrolled in each dose cohort based on a standard Phase 1 dose escalation scheme. Each patient will participate in only 1 dose cohort. The total number of patients to be enrolled in the Dose Escalation/Confirmation Phase is dependent upon the observed safety profile, which will determine the number of patients per dose cohort, as well as the number of dose escalations required to achieve the MTD or RP2D.

A starting sample size of at least 3 patients per dose cohort, expanding to 6 patients in the event of a marginal DLT rate (33%) was deemed to be a safe and conventional approach in the dose escalation of a novel oncologic agent. Assuming a true DLT rate of 5% or less, there would be a 3% chance that dose escalation would be halted in a given cohort (i.e., observing 2 or more patients with DLT). If a true DLT rate of 50% is assumed, then there would be an 83% chance that dose escalation would be halted in a given cohort.

A total of 9- additional patients will be enrolled in the Dose Confirmation Cohort to obtain additional AE, immune correlate, and anti-tumor activity data on entinostat at the MTD or RP2D in combination.

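### At 1 DLT in 3 patients the escalation sentence permits the next dose by count and labels the dose too toxic by percentage, where the plan's 3+3 requires three more patients

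*Protocol*

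**What the plan says.** The rule stands in the Synopsis under Study Design (Dose Escalation) and again in Protocol 8.2.1.1: "If <33% patients within a cohort have a DLT (i.e., <2 of up to 6), then enrollment of the next cohort may commence", subject to approval by the sponsor's study physicians in consultation with the investigators. The matching clause sets 33% or more, glossed as at least 2 of up to 6, as the point where the DLT dose level is reached. Section 8.2.1.1 adds the consequence: "then the DLT dose level will have been reached and the previous lower dose level will be considered the MTD".

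Other places describe the design this sentence is meant to implement:

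- The Synopsis says Phase 1b "employs a classical 3+3 design, with the determination of DLT and the MTD and/or RP2D". Section 5.1 names the same design, and Section 5.3 enrols 3 to 6 patients "in each dose cohort based on a standard “3+3” Phase 1 dose escalation scheme".
- The Synopsis sample size text starts each cohort with at least 3 patients, "expanding to 6 patients in the event of a marginal DLT rate (33%) or to confirm a dose for the Confirmation Phase". Section 12.1.1 and SAP 2.3.1 also give the expansion at 33%.
- Those same three places define a halt as at least two patients with a DLT. They put its probability at 3% for a true DLT rate of 5% or less and at 83% for a true rate of 50%.
- Section 8.2.1.1 alludes to expansion ("If a DLT necessitates enrollment of additional patients into a cohort") but does not say how many DLTs trigger it.

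**The concern.** The sentence offers two outcomes, escalate or DLT level reached. A 3+3 has a third, which is to expand the cohort, and it exists for the result 1 of 3. At that result the sentence's two tests point in different directions, and neither gives the expansion that the sample size text requires at the same 33%.

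This is a safety decision threshold, and Section 8.2.1.1 is where a site or study physician would look it up. Someone relying on the count there could open 5 mg after 1 DLT in the first three patients at 3 mg, before three more had been observed. Someone relying on the percentage could declare the dose too toxic; at 5 mg that would make 3 mg the MTD.

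**Working it through.** **Inputs.** Cohorts of 3 to 6 and expansion at a 33% rate (Synopsis, Sample Size Considerations; 12.1.1; SAP 2.3.1). Escalate below 33% or below 2 DLTs (Synopsis; 8.2.1.1). Stated halting probabilities of 3% and 83% (the same sample size sections). Let X be the DLTs in the first 3 patients, Y the DLTs in the next 3, and p the true DLT rate, with independent binomial outcomes.

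**Step 1: reproduce the plan's figures.** For a 3+3 that expands at 1 of 3, P(halt) = P(X≥2) + P(X=1)·P(Y≥1).

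- p = 0.05: 0.0073 + 0.1354 × 0.1426 = 0.0073 + 0.0193 = 0.0266, against a stated 3%.
- p = 0.50: 0.5000 + 0.3750 × 0.8750 = 0.5000 + 0.3281 = 0.8281, against a stated 83%.

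**Step 2: see whether another rule fits as well.**

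| Rule | P(halt), p = 5% | P(halt), p = 50% |
|---|---|---|
| Stated in the plan | 3% | 83% |
| 3+3 with expansion at 1 of 3 | 2.66% | 82.81% |
| Six patients from the start, halt at 2 or more | 3.28% | 89.06% |
| Count followed literally: P(X≥2) | 0.73% | 50.00% |
| Percentage followed literally (hypothetical): P(X≥1) | 14.26% | 87.50% |

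Of the rules tried, only the 3+3 with expansion matches both figures. The percentage row serves only to identify the rule used; it is not an estimate of risk.

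**Step 3: find where the two tests disagree.** Comparing x/n ≥ 0.33 with x ≥ 2 for every x and n from 3 to 6, the only disagreement is x = 1, n = 3 (33.3% meets the percentage; 1 is below 2). At six patients they agree: 1 of 6 is 16.7% and escalates, 2 of 6 is 33.3% and stops.

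**Step 4: size of the count reading.** It changes a cohort's decision when the first three have 1 DLT and the next three would have had at least one: P(X=1)·P(Y≥1).

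| True DLT rate | P(X=1) | P(Y≥1) | Escalates where the 3+3 would stop |
|---|---|---|---|
| 5% | 0.1354 | 0.1426 | 1.9% |
| 20% | 0.3840 | 0.4880 | 18.7% |
| 33% | 0.4444 | 0.6992 | 31.1% |
| 50% | 0.3750 | 0.8750 | 32.8% |

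These are upper bounds. They assume that the sentence is followed without regard to the sample size sections or the approval step.

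**Step 5: check that the repaired rule leaves the stated figures alone.** Stopping as soon as a second DLT occurs among up to 6 patients, with expansion at 1 of 3, is the same halting event as in Step 1. P(halt) stays at 2.66% and 82.81%.

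**The case against.** The best defence is that the count explains the percentage, so 33% is shorthand for 2 of 6, and that the sample size sections confirm this by defining a halt as at least two DLTs. On that view the protocol excludes stopping at 1 of 3. The escalation clause is also permissive and needs sponsor approval, so it does not forbid expanding first. Section 8.2.1.1 has the safety data of an enlarged cohort reviewed once all its patients have completed Cycle 1. The passages can then be read as successive steps of one 3+3.

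Much of this stands. The stop reading is largely ruled out, and for that reason no decision-change probabilities are given for it. A reader might infer an unresolvable three-way contradiction, or that the expansion step was left out of the plan. The documents support neither: the step is stated in three places, and the plan's own probabilities depend on it.

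The defence does not make the sentence consistent. It cannot apply only to completed cohorts of six, because a cohort with 0 of 3 moves up through the same sentence. At 1 of 3 it permits escalation and says nothing of expansion, and Section 8.2.1.1 never gives the trigger.

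It is also fair to say that the larger figures in Step 4 are remote. The count reading matters mainly at 3 mg, which Section 4.3.1 describes as a low dose, and nothing in the documents suggests true DLT rates of 33% or 50% there.

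**Conclusion.** The escalation sentence is wrong as written for one result, 1 DLT in 3 patients. The intended rule is clear from the rest of the plan. Severity is minor.

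The main literal risk is the count reading at 3 mg: at most 1.9% of cohorts at a true DLT rate of 5% and 18.7% at 20%, assuming independent outcomes and a reader who uses only this sentence. At 5 mg no higher dose is planned, and six patients must be treated at a dose before Dose Confirmation on any reading (Synopsis; 5.1). Nine confirmation patients follow. An intermediate dose level, which the protocol allows, would meet the same wording.

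Escalation appears complete. SAP 2.3.1 describes Cohorts 2 and 3 as having entered their second stage, and SAP 3.1.1 refers to dose-determination patients who received 5 mg.

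A reader might also infer that the 3% and 83% are miscalculated, that the MTD definition fails, or that the wrong dose went into Phase 2. The first is refuted by Step 1. The second does not follow, because the MTD definition (8.2.1.3) and the RP2D sentence work as written at six patients. On the third, the documents do not report whether any cohort had 1 DLT in its first three patients.

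**What to change.** Replace the percentage with counts in the Synopsis and in 8.2.1.1:

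- 0 of 3: escalate.
- 1 of 3: add up to three patients, and make no escalation decision until they complete Cycle 1.
- 2 or more DLTs at any point among up to 6 patients: stop.
- No more than 1 of 6: escalate.

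The third line should keep the words for any point among up to 6, so that a second DLT in the fourth or fifth patient still stops the cohort, as the current text does. The sample size, the 3% and 83%, the MTD definition and the RP2D sentence all stay. The cost is one sentence in each of two protocol sections.

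If no amendment is planned, state in the study report which rule was applied to any cohort with 1 DLT in its first three patients. The DLT proportion per dose cohort already planned (12.4.7; SAP 3.10.1) would not show this, because 1 of 6 does not reveal when the DLT occurred or why the cohort was enlarged.
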